#### **7.4 Day 15 Phone Contact**

Participants will be contacted by telephone at Day 15 ( $\pm 2$ ) of exemestane treatment by the study coordinator or designated study team member. The purpose of this contact is to query for exemestane-associated side effects/adverse events, review of the pill diary to confirm compliance, review any new or changes to medications and answer any questions the participant may have. It will be reiterated that the participant should continue exemestane daily with the last dose the day before surgery. In addition, the participant will be reminded to place the tampon (provided to her at the baseline (pre-surgical) clinic visit) 8-12 hours before the surgery.

#### **7.5 One Day (-2 days) Prior to Surgery**

The study coordinator or designee will again contact the participant and remind her to insert the tampon in her vagina 8-12 hours before the surgery and to bring her exemestane bottle(s) with any leftover tablets and the pill diary with her on the day of surgery. If her surgery is in the afternoon, she will be instructed to place the tampon the morning of her visit. Also, a review of exemestane associated side effects/adverse events, review of the pill diary to confirm compliance and review any new or changes to medications.

**For EOG site only**, the participant would return to clinic for this visit. The research nurse will place the tampon for surgery visit.

#### **7.6 Final Study Visit – Day of Surgery**

The surgical procedure will be standard of care and not altered based on participation.

The following research procedures will occur prior to surgery:

- Physical exam with vitals including height, weight and body mass index
- Medical/ surgical history review and update
- Review of concomitant medications and adverse events.
- Laboratory tests will include CBC with a differential, CMP, estradiol and progesterone.
- Appendix E: follow-up tobacco and alcohol assessment questionnaires will be administered.
- The vaginal tampon, which was placed by the participant 8-12 hours before surgery will be removed in the operating room by the surgeon prior to the surgical procedure. Attempt should be made to obtain tampon specimen at day of surgery visit even if baseline sample was not obtained.
- Research blood sample to obtain plasma pharmacokinetics of exemestane

At the time of surgery, once the patient is under anesthesia the vaginal tampon will be removed and processed in the same way as the pre-treatment tampon. The tampon will be processed at each institution and the resultant cells and washings will be frozen and shipped on dry ice to the University of Minnesota for DNA and protein extraction per section 10.2.

The surgical pathologic specimen (the uterus) will be processed as is the usual standard at each institution. A portion of the FFPE tumor block will be collected and batch shipped to UMN at the end of the study to be cut into 10 unstained 5 $\mu$ m slides. If the FFPE block cannot be sent due to limited amount of tumor, then 10 unstained 5 $\mu$ m slides will be cut and the slides will be shipped to UMN. An additional section of the tumor, up to 1x1x1cm, will be collected after removal of the uterus or from the pathology lab, cut in half and snap frozen as per institutional policy for genetic and protein analysis. If there is not a visible lesion, select a random 1x1x1 cm from the endometrium, or smaller if the pathology team needs to review more of the endometrium. This is done at the investigators clinical discretion. This tumor section will also be batch shipped to UMN at the end of the study. The tumor biopsy specimens, the FFPE blocks and the

unstained slides will be sent to the University of Minnesota (UMN) for proteomics, DNA analysis, histologic review, and IHC.

The study coordinator or designee will collect the exemestane supply and completed drug log.

### **7.7 Follow-up Contact**

The final study visit will coincide with the day of surgery unless there are any unresolved AEs (with a possible, probable or definite attribution to the study agent) on the day of surgery. The unresolved AEs will be assessed via telephone call during the postoperative period, before or on the day of the 1st post-surgical follow-up visit. AEs that occurred after surgery will not be recorded.

**For EOG site only**, follow-up at the standard of care post-operative visit will be performed in order to collect long-term safety information of the study treatment, whether or not the participant has any ongoing adverse events at the surgery visit.

## **8. CRITERIA FOR EVALUATION AND ENDPOINT DEFINITION**

### **8.1 Primary Endpoint**

Estrogen stimulates the proliferation of endometrial cells; we hypothesize that blocking the enzyme aromatase will lead to less estrogen available to stimulate the growth of pre-cancer and cancerous endometrial cells. Thus, exemestane treatment should lead to decreased levels of Ki-67, an important marker of cellular proliferation.

Unlike in breast cancer, proliferation indices in endometrial cancer are not well study and a threshold that predicts ongoing response to Aromatase Inhibitor therapy does not yet exist. Choosing a threshold at which to power this study would be arbitrary. Our goal is to help begin to establish these important biomarkers in endometrial cancer. Therefore, the primary endpoint of the study is the absolute change in proliferation index (Ki-67) expression in CAH/EIN or low grade (grade 1 and grade 2) endometrial cancer cells from baseline to post-exposure. We will evaluate the change from baseline to post-exposure in absolute change in percent Ki-67 using one-sample Student's t-test or Wilcoxon signed-rank test, as appropriate. Immunohistochemistry will be performed at the UMN Histology and IHC Laboratory and then read by [name].

Tissue collected from the research biopsy and surgical specimen will be fixed in 10% neutral buffered formalin and processed into paraffin blocks. Antigen retrieval is performed on slides using a 6.0 pH buffer in a steamer, followed by a cool down period. Slides are rinsed in water followed by immersion in 1x Tris-buffered saline/0.1% Tween-20 (TBST). Subsequent steps are automated using an IHC staining platform (Nemesis, Biocare). Endogenous peroxidase activity is quenched by slide immersion in 3% hydrogen peroxide solution followed by TBST rinse. A serum-free blocking solution is placed on sections. Blocking solution is removed and slides are incubated in primary antibody diluted in 10% blocking solution/90% TBST followed by TBST rinse. A two step polymer detection (Novalink, Leica) is used according to manufacturer's instruction. Following the detection, the slide is rinsed with TBST and diaminobenzene is applied followed by TBST rinse. Slides are then counterstained with CAT Hematoxylin (Biocare) rinsed, dehydrated and coverslipped.

### **8.2 Secondary Endpoints**

#### **8.2.1 Circulating serum estradiol and progesterone:**

Evaluate pre and post treatment circulating serum estradiol and progesterone levels to determine the effect

of a daily dose of 25 mg of exemestane for 21-42 days.

### **8.2.2 Pathological response (regression of CAH/EIN and low grade (grade 1 and grade 2)endometrial carcinoma):**

Examine pathologic changes in CAH/EIN or carcinoma from pre-treatment biopsies to final pathology. Ultimately, the goal of any pharmacologic intervention will be regression of CAH/EIN and low grade endometrial carcinoma to a normal endometrium. Given that the average time for regression for progesterone therapy is approximately 6 months, we do not anticipate that 3 weeks of exemestane therapy will result in high levels of tumor regression. However, we do anticipate that there may be some change in histology. All preoperative biopsy specimens and postoperative surgical specimens will undergo H&E staining. Central pathology review will be performed by [name] at the University of Minnesota. Review will be in accordance with the updated pathologic criteria.

### **8.2.3 Tissue biomarkers:**

Examine biomarker differences in pre and post treatment samples with regards to expression (measured by immunohistochemistry) of markers of these cellular functions or pathways.

- a) Apoptosis (cleaved caspase 3)
- b) Proliferation (cyclin D1)
- c) Insulin pathway (pAKT, IGF-1R)
- d) Endocrine regulation (ER/PR/AR)

Estradiol induces the production of IGF-1 and the expression of IGF-1 receptor (IGF-1R) is higher in the endometrium of patients with CAH/EIN and endometrial cancer compared to normal endometrium^30 Thus, our hypothesis is that by using exemestane to reduce the levels of systemic estradiol, this will lead to lower levels of IGF-1 and reduced IGF-1R expression. Activation of IGF-1R by IGF1 leads to phosphorylation of AKT through the PI3K/AKT pathway, which in turn causes accumulation of nuclear cyclin D1, leading to increased mitosis and cellular proliferation in addition to having a potent anti-apoptotic effect. Therefore, reducing IGF-1R activation by decreasing estradiol will lead to decreased pAKT, cell cycle arrest, and increased apoptosis. We hypothesize that exemestane will not only show a decrease in cellular proliferation as evidenced by a decrease in Ki-67, but a decrease in the cell cycle regulatory protein, cyclin D1, and lead to an increase in cleaved caspase 3, which is a marker of apoptosis. We also hypothesize that due to exemestane's inhibition of androgen binding sites and subsequent effects on hormone levels, there may be a change in hormone receptors (estrogen, progesterone and androgen receptors), as measure by IHC. The following biomarkers, all of which are commercially available, will be assessed: Cyclin D1, cleaved caspase 3, pAKT, IGF-1R, ER-alpha, PR, AR. Staining technique will be as above.

### **8.2.4 DNA mutational analysis through Next Generation Sequencing and methylation status of endometrial tumor and vaginal DNA:**

Analyze DNA from the CAH/EIN or low grade endometrial carcinoma for specific genetic mutations, microsatellite instability and hypermethylation in order to correlate exemestane response to mutational status. Additionally, vaginal DNA (recovered from tampon collection) will be analyzed for presence of tumor mutations or hypermethylation.

**8.2.4.1 Tumor genetics:** As evident by the recent TCGA analysis of >350 endometrial carcinomas, endometrioid tumors have frequent mutations in a variety of genes including PTEN, CTNNB1, PIK3CA, KRAS, and POLE. Furthermore, the TCGA categorized endometrial carcinoma into 4 prognostically significant groups characterized by; 1) POLE hotspot mutations and endometrioid morphology; 2) microsatellite instable (MSI) tumors with mutated PTEN and endometrioid morphology; 3) microsatellite

stable (MSS) tumors with mutated PTEN and endometrioid morphology; and 4) MSS tumors with mutated TP53, high somatic copy number alteration burden and predominantly serous or mixed morphology. We hypothesize that response to exemestane may correlate with tumor genetics and these described subtypes. We therefore seek to determine the mutational status of all tumors with DNA panel testing to see if this correlates with treatment response. In this context, tumor response will be defined as any decrease in absolute Ki-67 expression by  $\geq 5\%$ .

Pre and post treatment specimens will be sent to the MDL for DNA extraction from AllProtect or fresh frozen tissue. Mutation testing will be performed via Next Generation sequencing using a CLIA-validated 62 gene solid tumor panel. This panel includes clinically actionable genes identified from high quality somatic mutation databases including the Dienstmann, DOCM, MD Anderson Personalized Cancer Therapy, and My Cancer Genome databases. All cases from the TCGA dataset demonstrated at least one mutated gene from this 62-gene panel and the critical genes needed for subtype assessment (POLE, PTEN, TP53) are covered within it. DNA will be extracted using the QIAamp DNeasy Tissue kit (Qiagen. Inc). DNA will be quantified using Qubit reagents (ThermoFisher) and target specific enrichment will be performed using the Fluidigm Access Array microfluidics PCR system. Sample specific barcodes are appended in a second step PCR reaction, pooled, and sequenced on a MiSeq instrument (Illumina). Raw sequencing data is analyzed through a validated custom bioinformatics pipeline. Average coverage is  $>2000X$ , and limit of detection sensitivity is 5% variant allele fraction (VAF) for single nucleotide variants (SNV) and 1% VAF for indels.

Microsatellite instability will be assessed using the NCI recommended 5 marker panel. DNA from tumor and matched normal tissue (if available) will be PCR amplified (GeneAmp® PCR Reagent Kit Applied Biosystems) with fluorescently labeled primers for the 5 variable marker regions and separated by capillary electrophoresis (Applied Biosystems 3100 Genetic Analyzer). Cases will be categorized as MSI-high if 3 or more markers are shifted, MSI-low if 1 or 2 markers are shifted, and MSS if zero markers are shifted.

**8.2.4.2 DNA Recovery from Tampon Experiments:** Given that the endometrium communicates with the vagina through the endocervix, we speculate that we could identify protein and DNA that descend through the endocervix and into the vagina through tampon collection, based on a recently published manuscript on DNA recovery from vaginal tampons for the detection of ovarian cancer. This ovarian cancer detection study focused primary on identifying tumor specific somatic DNA through deep sequencing of vaginal DNA. In this present study, we propose a similar method of DNA collection for cancer detection through tampon recovery.

Tampons will be collected in the clinic or operating room and will be placed into a 50 mL conical polypropylene tube with a screw-top lid into which 30 mL of cold, sterile phosphate buffer saline (PBS) will be added. The tampon can soak in the cold PBS solution for up to 12 hours before agitation. The tube will be mounted on a platform rocker for 30 minutes at 4°C for gentle agitation. The tampon will be carefully removed from the conical tube and inserted into a 35cc syringe. The plunger of the syringe will be slowly depressed to completely compress the tampon, thereby releasing cells and any of the remaining PBS solution from the tampon. The tampon will then be discarded. The PBS solution that was in the initial conical tube with the tampon should be combined with the PBS solution that was compressed out of the tampon to yield approximately 30 mL. This 30 mL cell suspension will be equally divided into two 50 mL conical polypropylene tubes and centrifuged for 10 minutes to pellet the cells. The 14 mL of supernatant from both of the conical tubes will be gently removed by pipet and combined into one conical polypropylene tube. The cell pellets will be re-suspended in the remaining 1 mL of PBS using a disposable glass pipet and transferred to 1.5 mL Eppendorf tubes each and spun for 10 minutes at 3000xg. After separating the cell pellets the remaining 1 mL of supernatant from both tubes will be combined with the supernatant in the 50 mL conical polypropylene tube. This will be frozen and shipped on dry ice to the University of Minnesota.

The cell pellets that remain at the bottom of the two 1.5 mL Eppendorf tube will be frozen and shipped to the University of Minnesota on dry ice.

DNA will be extracted from the cell pellet using a modified protocol and reagents from the QIAamp DNA mini kit (Qiagen) as previously described by Erickson et al. DNA concentration will be quantified using Qubit reagents (ThermoFisher). Extracted DNA will be used to identify genomic alterations observed in tumor DNA. We will modify the 62-gene solid tumor NGS assay (or a subset of genes enriched for mutations in the study population) for this purpose to incorporate unique identifiers (UIDs) as described by Kinde et al.. Our laboratory has extensive experience using amplicon based enrichment on the microfluidics platform for enrichment of targets using NGS. Using a combination of both microfluidic PCR and UIDs, we anticipate capability to detect somatic alterations at least as low as 0.01% in the tampon DNA which will be compared to matched sequencing of the concurrent endometrial biopsy specimen.

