## **3. SUMMARY OF STUDY PLAN**

**Study Plan:** This is a multi-center, phase IIA, single-arm ‘window of opportunity’ pilot study of 25 mg per day of exemestane for 21 to 42 days in patients undergoing hysterectomy for CAH/ EIN or low grade endometrial cancer (grade 1 or grade 2). Tissue from participant’s research endometrial biopsy will be used for pre-surgical biomarker analysis. The tissue obtained from surgical excision will be used for post-treatment biomarker analysis.

Study recruitment will occur in gynecology oncology clinics at participating institutions. A lead gynecologic oncology surgeon has been identified at each site. Up to 40 patients will be accrued for this pilot study. An age, disease and body mass index (BMI) matched historical comparator cohort will also be identified in order to compare changes in the primary outcome, Ki-67 expression between biopsy and surgical specimen in an untreated cohort.

For the U.S. based sites, prior to the baseline (pre-surgical) clinic visit, a pre-screening telephone contact will be completed to determine interest and basic eligibility for the study. If the participant gives verbal consent, study materials will be mailed to them. Materials will include a full study consent form to read through prior to their visit as well as 2 tampons (one to be inserted prior to the baseline (pre-surgical) clinic visit and other one as back up) and instructions for inserting the tampon (appendix D).

At the baseline (pre-surgical) clinic visit, participants will meet the study team to discuss and sign the informed consent form. The study team (including the research coordinator and the treating gynecologic oncologist) will review their medical history, conduct physical examination and review of concomitant medications. Participants will also have baseline laboratory tests. These tests include Complete Blood Count (CBC) with differential and platelets, Comprehensive Metabolic Panel (CMP), Estradiol, Progesterone and Follicle Stimulating Hormone (FSH) in all women 45-55 years old and in women 56-59 years old if they report less than 2 years of amenorrhea to confirm the post-menopausal status. Additionally,

blood will be drawn for exemestane pharmacokinetics. This research blood sample for exemestane pharmacokinetics will be destroyed if the participant does not qualify for the study.

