#### **8.2.4.3 DNA Methylation**

To better define the sensitivity of vaginal DNA methylation in the detection of endometrial cancer, an additional experiment whereby vaginal DNA extracted through tampon collection will be evaluated for hypermethylation. DNA from the corresponding endometrial tumor (low grade endometrial carcinoma or CAH/EIN) will be separately analyzed and the tumor DNA-vaginal DNA pairs will be analyzed for concordance of methylation across 850,000 CpG sites. Vaginal DNA will be extracted per methods already described for the genomics portion of this study from the cell pellets. The same DNA extracted from the cell pellet will be used for NGS. A bisulfite conversion step will be performed as part of the standard Illumina Methylation array protocol, which requires 250 ng minimum DNA input. Vaginal and tumor DNA methylation studies will be performed using the EPIC methylation chip (Illumina Inc.), which evaluates methylation in 850,000 CpG sites that include both promoter and enhancer elements using 500 ng of DNA.

The proposed experimental design will accomplish several novel goals. First, this design will establish the global methylation pattern of each patient's endometrial carcinoma/EIN which can be statistically compared to the primary study endpoint (Ki-67 response to exemestane treatment) in the context of potentially clinically relevant methylation groups established by the TCGA. Second, the design will allow to rigorously test the sensitivity/limit of detection for specific methylation pattern discrimination in the tampon DNA for underlying carcinoma. Finally, the design will allow for a robust comparison of clinical utility between ultra-sensitive DNA sequencing, methylation analysis, and proteomics to determine which platform is most sensitive for detection of disease.

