pellets). We will provide these samples to the University of Minnesota Genomics Center, whose staff will run the samples as a fee-for-service. 1- send Olink ~50 ug of protein from the 40 tampon washing samples (10 pre-surgery supernatant, 10 post-surgery supernatant, 10 pre-surgery cell pellets, and 10 post-surgery cell pellets). 2- Once optimal dilutions have been determined, we will be able to test the other 4 Olink panels that are relevant to this study as a fee-for-service.

SomaLogic technology was also initially designed to quantify the levels of proteins in sera and/or plasma. However, SomaLogic uses technology based on aptamers to quantify protein levels in many types of samples (See their website at <https://somalogic.com/>). Their technology allows for the quantification of 7000 proteins simultaneously from 75 ul of protein at 0.2 ug/ul.

We propose to: 1- Send SomaLogic ~10 ug of protein from the 40 tampon washing samples (10 pre-treatment supernatants, 10 post-treatment supernatants, 10 pre-treatment cell pellets, and 10 post-treatment cell pellets). 2- As a fee-for-service, have SomaLogic run the 40 samples on their SomaScan platform.

Once we have the data back from Olink and SomaLogic, we will be able to analyze the data to identify proteins that are differentially expressed between the tampon supernatants and cell pellet lysates, the pre- and post-treatment samples from the same patient, as well as those proteins that are differentially expressed between the women whose tumors respond to Exemestane treatment and those whose tumors do not respond.

Since the Olink and SomaLogic platforms are not compatible with denatured proteins, it will not be possible to use either platform to analyze the protein extracts from the biopsies (which were extracted in AllPrep reagent for recovery of DNA and protein) or tumor tissues. The tissue sample extracts can be used for other protein experiments, such as validation of the proteins identified in the tampon washing samples by Western immunoblotting.

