Option 3 of this project is to analyze a subset of the samples from the remaining 30 patients by proteomic techniques in a similar manner to those outlined above for Patients #1-10. In particular, based on the results that we obtain from the Proteomic Pilot study using 10 patients and 40 samples, we will be able to limit our next set of experiments to the one sample type (tampon washing or tampon cell pellet) that provided the best results, instead of analyzing all of the remaining 120 samples (i.e. 30 remaining patients x 4 samples each). For example, we would omit a sample type(s) that did not yield sufficient protein after removal of the highly abundant proteins. Or we may omit the sample type(s) that did not show any significant differences in proteins identified or quantified between the pre-treatment and the post-treatment. We may also decide to limit the samples to cases where the women responded to treatment. Thus, we will limit Option #3 to the analysis of an additional 30 samples. Thus, the cost of performing the experiments in Option #3 would cost the same as the experiments outlined in the Proteomic Pilot study. The data from these experiments will allow us to make comparisons between the sample sets and validate our results.

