### 13.5 Secondary Objectives, Endpoints, Analysis Plans

The secondary objectives are to examine and test change in circulating serum estradiol and progesterone, histology, and tissue biomarkers. Additionally, we will correlate response with tumor DNA mutations, and

protein and DNA markers via tampon recovery. Therefore, the secondary endpoints are the changes in circulating serum estradiol and progesterone levels, in tissue biomarkers such as apoptosis as measured by cleaved caspase 3 level, proliferation as measured by cyclin D1 level, and insulin pathway as measured by pAKT and IGF-1R levels, and hormone receptor changes as measured by ER, PR and AR.

All tumors will be sequenced via Next Generation Sequencing panel testing and also be tested for microsatellite instability. Results of tumor genetic testing will be correlated with exemestane response as defined by the change in Ki-67 expression.

As an exploratory endpoint, we will attempt to identify the genetic mutation of the primary tumor by performing Next Generation Sequencing of tampon collected DNA. Additionally, vaginal proteomic analysis will also be performed via tampon collection and correlated with tumor response to exemestane as defined by the change in Ki-67 expression.

To evaluate the reliability of methylation measurement assayed on the 850K EPIC chip, an intraclass correlation coefficient (ICC) will be calculated for each CpG site using the technical replicates (using 4 blinded duplicate measurements). We aim to classify the CpG sites into multiple reliability groups, by modeling the distribution of ICC values using a mixture distribution.

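### The tumor-genetics correlation cuts Ki-67 change at a 5% fall without a reason and loses power; the proteomic work forms responder groups with no rule, where the continuous change would serve both

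*Combined protocol and SAP*

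**What the plan says.** Section 8.1 states that "the primary endpoint of the study is the absolute change in proliferation index (Ki-67) expression" from baseline to post-exposure. The tissue is planned for every participant: a research biopsy before treatment, and for the later value "The tissue obtained from surgical excision will be used for post-treatment biomarker analysis" (section 3).

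The secondary and exploratory correlations do not treat response in one way:

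- **Tumor genetics, 8.2.4.1.** "In this context, tumor response will be defined as any decrease in absolute Ki-67 expression by" 5% or more. No citation or reason follows.
- **Tumor genetics, 13.5.** "Results of tumor genetic testing will be correlated with exemestane response as defined by the change in Ki-67 expression". No cut and no test are named.
- **Proteomics, 13.5.** Vaginal proteomics will be "correlated with tumor response to exemestane as defined by the change in Ki-67 expression". Again there is no cut.
- **Proteomics, 8.2.5.** The analysis will look for "those proteins that are differentially expressed between the women whose tumors respond to Exemestane treatment and those whose tumors do not respond". For the later samples (Option 3) it adds: "We may also decide to limit the samples to cases where the women responded to treatment". The section does not say who is a responder.
- **Methylation.** Section 8.2.4.3 gives tumor methylation "which can be statistically compared to the primary study endpoint (Ki-67 response to exemestane treatment") as its comparison. Section 13.5 relates vaginal methylation to the primary endpoint, change in Ki-67, by linear mixed models.

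**The concern.** Cutting a continuous measurement discards information. A woman whose Ki-67 falls by 6 points counts the same as one whose Ki-67 falls by 20, and falls of 4 and 6 are treated as opposites. With about 30 evaluable women there is little information to spare, and the uncut change is already the primary endpoint.

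The proteomic plan raises a second matter. If responder groups are needed but not defined, the dividing line can be drawn after Ki-67 results are known. If later samples come only from responders, the range of Ki-67 change is truncated, and no non-responders remain for comparison in that set.

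**Working it through.** **Inputs from the plan.** Evaluable women: 30 (13.1). SD of change 7.5, and detectable mean fall 3.8 at 0.85 power (13.4). Cut: 5 (8.2.4.1), read here as percentage points.

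**Assumptions, none given in the documents.** A marker divides the women 15 v 15 or 9 v 21. Carriers have the larger fall, by d = 7.5 or 3.75 points. Changes are normal, with an overall mean fall of 3.8. Tests are two-sided at 0.05: two-sample t on the change, uncorrected chi-square on the cut.

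**1. The plan's own figure.** One-sided one-sample t, n = 30, effect size 0.50: noncentrality 0.50 × √30 = 2.739, critical value 1.699 on 29 df, power 0.848. The plan states 0.85, so it reproduces. The cut does not enter this calculation.

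**2. Group means.** With carrier share w, carriers fall by 3.8 + (1 − w)d and non-carriers by 3.8 − wd. At d = 7.5 this gives 7.55 and 0.05 (15 v 15), or 9.05 and 1.55 (9 v 21).

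**3. Power on the continuous change.** Noncentrality = d / [s√(1/n1 + 1/n2)], 28 df, critical value 2.048. With within-group SD s = 7.5:
- 15 v 15: 7.5 / (7.5 × 0.365) = 2.739, power 0.753.
- 9 v 21: 7.5 / (7.5 × 0.398) = 2.510, power 0.678.

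**4. Power on the cut.** The share of responders is Φ[(mean fall − 5)/s]: 63.3% v 25.5% (15 v 15) and 70.5% v 32.3% (9 v 21). Summing the binomial probabilities of all tables that chi-square rejects gives 0.554 and 0.513. The actual size of that test at a common response rate of 43.6% is 0.047 and 0.053, so the loss is not caused by a conservative test. (Fisher's test gives 0.387 and 0.458, but part of that drop is its small size, so it is not used here.)

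**5. If 7.5 is the overall SD.** Section 13.4 gives the SD for treated low-grade patients as a whole. Holding the overall SD at 7.5, s = √[7.5² − w(1 − w)d²]. At d = 7.5 this is √(56.25 − 14.06) = 6.50 (15 v 15) and √(56.25 − 11.81) = 6.67 (9 v 21).

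| Marker difference | Split | SD of 7.5 taken as | Power, continuous | Power, cut |
|---|---|---|---|---|
| 7.5 | 15 v 15 | within group | 0.75 | 0.55 |
| 7.5 | 9 v 21 | within group | 0.68 | 0.51 |
| 7.5 | 15 v 15 | overall | 0.86 | 0.68 |
| 7.5 | 9 v 21 | overall | 0.78 | 0.61 |
| 3.75 | 15 v 15 | within group | 0.26 | 0.18 |
| 3.75 | 9 v 21 | within group | 0.23 | 0.18 |

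**6. Scale of the loss.** With within-group SD 7.5 and d = 7.5, the cut first reaches 0.753 at 23 women per group (0.764; 22 gives 0.732), against 15 for the continuous change. At an illustrative 0.05/62 = 0.00081 for the 62-gene panel, power at 15 v 15 is 0.19 v 0.08.

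**7. What a responder count shows.** With mean change 0 and SD 7.5, the share falling by 5 points or more is 1 − Φ(5/7.5) = 25%. The count alone is not evidence of an effect.

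**8. Proteomics.** The only Ki-67 responder rule in the documents is in 8.2.4.1, and its opening words limit it to the tumor-genetics setting. Section 8.2.5 does not refer to it, and 13.5 ties proteomics to the change without a cut. The groups in 8.2.5 therefore have no stated rule.

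**The case against.** A reader might infer that 8.2.4.1 and 13.5 contradict each other, or that the genetics variable is open to choice after the data are seen. The documents do not support either reading. A fall of 5% or more is a response defined by the change in Ki-67, so 13.5 can be shorthand for 8.2.4.1, which sets its cut in advance. Nor does 8.1 contradict the cut. Its remark that a threshold would be arbitrary concerns powering the study, although its statement that no predictive threshold yet exists shows why a cut needs a reason.

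A simple responder label is a legitimate device in hypothesis-generating work, and a reader could carry the 8.2.4.1 rule into 8.2.5. One cross-reference would then settle who is a responder. That is fair, but the cross-reference is absent and would still leave the less efficient variable in place. Option 3 is conditional, in work the plan calls exploratory.

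The power figures rest on assumed marker differences, splits and normality, while 8.1 and 13.4 leave the Wilcoxon test open. The 7.5-point case is a large effect: at 15 v 15 with within-group SD 7.5, it means almost no fall in non-carriers. At 3.75 points, or after allowance for 62 genes, neither approach has much power, and the choice would seldom change a conclusion. This limits the size of the point, but the continuous change has more power in every case computed.

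Methylation needs no change, because 8.2.4.3 and 13.5 already point to the primary endpoint.

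**Conclusion.** The point holds in two limited parts. For genetics, the plan uses a pre-specified but unexplained cut that is less efficient than the change it already measures. The loss is 0.17 to 0.20 in power for an assumed 7.5-point difference, under either reading of the SD, and 0.05 to 0.08 at 3.75 points with within-group SD 7.5, where power is low either way. For proteomics, responder groups and possible selection by response have no stated rule, so grouping after the fact is possible there and only there.

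The textual observations are firm. The power figures illustrate the loss and do not forecast the trial's results. Only secondary and exploratory analyses are touched; the primary test and the sample size stand. This is an improvement to consider.

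**What to change.** - **8.2.4.1 and 13.5:** make the continuous absolute change in percent Ki-67 the analysis variable for the mutation and MSI correlations, and add the word continuous in 13.5. Keep the count of women with a fall of at least 5 percentage points as a descriptive summary only.
- **8.2.5, comparison of responders with non-responders:** relate protein levels to the same continuous change, in line with what 8.2.4.3 and 13.5 do for methylation.
- **8.2.5, Option 3:** delete the possible restriction to women who responded. Select later samples by sample type only, so that the change can be analysed over its full range. One of the four sample types from each of the 30 remaining women gives 30 samples, the stated limit. If a type means washing or pellet at both time points, 30 × 2 = 60 exceeds that limit, and any reduction should follow a rule that ignores response, such as enrolment order.

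The cost is wording in three sections. No new visit, assay or Ki-67 reading is needed.
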